10. STATISTICAL CONSIDERATIONS

10.1. Sample Size Determination

The primary goal of hemophilia treatment is to reduce the bleeding rate or to achieve freedom from bleeding. As an approximation of the appropriate number of cases for the data collection accompanying the application, the Institute for Quality and Efficiency in Health Care (IQWiG) conducted the sample size calculation based on ABR for treated bleeds. Evaluation of the ABR is performed using a negative binomial model. The relative effect measure is the incidence rate ratio of Roctavian over SoC, which can be tested against the shifted null hypothesis of 0.5, assuming a significance level $\alpha = 2.5\%$ with a one-sided test, and power of at least 80%. Higher values for the ABR (parameter λ) stand for a worse outcome. Furthermore, a distribution of the Sample Roctavian vs. SoC of 1:5 is assumed (sample size ratio $\theta = 0.2$). Other required parameters are the Average Exposure Time ($u_t = 1$ year), the ABR for the SoC and Roctavian groups ($\lambda_{\text{SoC}} = 3$, $\lambda_{\text{Roctavian}} = 0.85$) and a value for the overdispersion ($\phi = 1.5$). This results in a total sample size of at least 397 participants (Roctavian Cohort $n = 67$, SoC Cohort $n = 330$) ([Zhu 2017](#)).

Based on current estimates of participant enrollment, the study will be powered based on the ABR approach. The sample size calculation is based on a shifted null hypothesis to add robustness to the generated evidence. However, the actual null hypotheses for testing all primary and secondary endpoints are not shifted.

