10.3.6. Primary Objective

10.3.6.1. Objective: To compare the annualized bleeding rate for treated bleeds.

Annual bleeding rates for treated bleeding events (see [Table 6](#)) will be compared between the Roctavian Cohort and SoC Cohort after PS adjustment. *A priori* the PS adjustment is planned to be implemented via IPTW. All participants with the variables recorded to derive the PS will be included in the analysis. Participants with no bleeds reported but data entered into the DHR will have an ABR of zero (ie, data is not considered missing).

ABRs will be compared over the full follow-up time for each participant in the study, as well as during annual increments during the follow-up. For analyses of annual increments, only those participants who have full follow-up for the time will be included in analyses. For example, analyses comparing ABRs during the first year will only include participants with ≥ 1 year of follow-up after the index date or analyses comparing ABRs through 2 years of follow-up will only include participants with ≥ 2 year of follow-up after the index date.

Sample sizes are expected to be reduced in analyses of annual increments for interim analyses as data collection will be ongoing, and potentially reduced for final analyses due to censoring (see below).

ABRs will be calculated for each participant as the number of bleeds divided by the time between the start of follow-up and censoring event for the analysis, annualized to the number in 1 year. The mean of the individual participant ABRs for each cohort will be calculated and compared. The primary comparison of ABRs will be based on the absolute difference in the mean treated ABR between the Roctavian Cohort and SoC Cohort utilizing a two-sample t-test (two-sided).

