7.9. Statistical Analysis Approaches

Descriptive statistics will be generated for all study measures. Descriptive statistics will include means, 95% CIs, SDs, medians, interquartile range (IQR), and minimum and maximum values for continuous variables and frequencies and percentages for the categorical variables. Univariate statistics will be calculated for each measure of interest. Baseline and outcome variables will be compared between the Roctavian and SoC Cohorts using chi-square tests for categorical variables, two-sided t-tests for continuous variables, and Wilcoxon rank-sum tests for medians of continuous variables if the continuous variables are not normally distributed.

For event-based outcomes including the bleeding outcomes, negative binomial models will be fit. Zero-inflated negative binomial models will also be considered if the outcomes show excess zeros (see Section 7.9.3 for details). For binary outcomes, logistic regressions will be fit. For continuous outcomes, general linear regression will be used, with appropriate transformation if needed to ensure model assumptions are met. For COAs, general linear mixed models to account for repeated measures are planned. All the models will be adjusted with propensity score weights and results will be reported based on observed values (before IPTW is applied) and the weighted values (after IPTW is applied).

To adjust for confounding, propensity scores will be calculated and applied using appropriate propensity score IPTW to ensure balance of covariates between the Roctavian and SoC Cohorts. Both unadjusted and propensity score adjusted results will be reported. IPTW is the primary propensity score method for adjustment of confounding. PSM will be performed as an *a priori* sensitivity analysis. Additional details on propensity score methodology is presented in Section 7.8. If additional covariate adjustment is required to balance the Cohorts, multivariable models will be reported.

P-values and SMDs will be reported for comparisons between Roctavian and SoC Cohorts. A p-value <0.05 will be considered statistically significant. All analyses will be based on observed, not projected, data. The sample size calculations are powered for the primary outcome (i.e., ABR), therefore, all p-values associated with secondary outcomes are nominal.

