7.9.3. Analysis of Primary Outcome

Population	Measurement Period	Analysis Notes
All participants For interim and analyses at fixed timepoints, only those with specified amounts of follow-up will be included	≥1 year of follow-up, ≥2 years of follow-up, ≥3 years of follow-up, all available follow-up	Participants with no bleeds will be included as having an ABR of 0

The primary objective to compare the ABR for treated bleeds between the Roctavian and SoC Cohorts will be measured by annualizing the number of bleeds reported in the DHR. Follow-up for ABR will begin as of the index date for the SoC and Roctavian Cohorts. Bleeds will be identified if participants have an “occasion” for treatment of spontaneous bleeding/hemorrhage (regardless of severity). Participants may have multiple bleeds during the reporting period. To calculate ABR, a count of the number of bleeds for each participant will be divided by the number of days in the relevant time period for each participant, multiplied by 365.25. The mean of the individual ABRs for each Cohort will be calculated and then compared between Cohorts over the full follow-up time, as well as during annual increments during the follow-up. For analyses of annual increments, only those participants with full follow-up for that timepoint will be included. For example, analyses comparing ABRs during the first year will only include participants with ≥1 year of follow-up after the index date or analyses comparing ABRs through two years of follow-up will only include participants with ≥2 year of follow-up after the index date. Sample sizes are expected to be reduced in analyses of annual increments for interim analyses as data collection will be ongoing.

Mean, SD, median, IQR, minimum and maximum will be reported for the primary outcome by study group. Histograms will be plotted for the primary outcome by study group. SMD will be calculated to compare Roctavian and SoC Cohort. The participant number in the two Cohorts will be weighted using IPTW generated from the propensity score model. Both unadjusted and propensity score adjusted results will be reported and compared.

Given treated bleeds are event based, a IPTW weighted negative binomial model will be fit to compare ABR between Roctavian and SoC Cohort, with negative binomial distribution and log link function, and the log transformed follow-up time as the offset variable. IPTW will be applied to create

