more similar Roctavian and SoC Cohorts. Other clinically significant prognostic factors or covariates that remain imbalanced after propensity score adjustment will be included in the model as well. Regression coefficients, corresponding 95% CIs and p-values will be reported for all explanatory variables included in the model. The estimated rate ratio (ABR in Roctavian Cohort / ABR in SoC Cohort) generated from the IPTW weighted negative binomial model will be tested against the shifted null hypothesis of 0.5. For an alpha=0.025 test, the shifted null hypothesis is rejected if the upper boundary of the two-sided 95% CI for the rate ratio is less than the null hypothesis 0.5. The CI of the estimated rate ratio will be calculated using the Wald method.²⁷

Given some participants may have no treated bleeds based on prior literature,⁴⁶ a two-part zero-inflated negative binomial model will also be considered. If the negative binomial model does not converge,⁴⁷ or if the AIC in the model accounting for zero-inflation is lower, then the zero-inflation negative binomial model will become the primary objective analytic model, as lower AIC indicates a better fit. For the zero-inflated negative binomial model, first the model will be fit for a binary outcome whether a participant had a treated bleed during the outcome assessment period, and then an ABR count outcome for treated bleeds among participants who had at least one treated bleed during the outcome assessment period (excluding participants with zero bleeds) will be fit. Finally, the unconditional ABR estimates for treated bleed will be calculated by multiplying the estimated conditional ABR from the count model by the probability of having a treated bleed estimated from the binary model for both the Roctavian and SoC Cohorts.

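### The primary test of treated ABR is defined two incompatible ways: a t-test of no difference in mean ABR, and a negative binomial rate ratio tested against 0.5

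*Protocol*

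**What the plan says.** Protocol 10.3.6.1 computes an ABR for each participant, averages these within cohort after propensity score adjustment, and makes the primary comparison "based on the absolute difference in the mean treated ABR between the Roctavian Cohort and SoC Cohort utilizing a two-sample t-test (two-sided").

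Protocol 10.1 sizes the study on the incidence rate ratio against 0.5 (one-sided 2.5%, power at least 80%) and states "Evaluation of the ABR is performed using a negative binomial model". It then limits the 0.5 to the sample size calculation: "However, the actual null hypotheses for testing all primary and secondary endpoints are not shifted".

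SAP 7.9.3, bound into the same file, says that "a IPTW weighted negative binomial model will be fit to compare ABR between Roctavian and SoC Cohort", with a log link and log follow-up time as offset. The rate ratio "generated from the IPTW weighted negative binomial model will be tested against the shifted null hypothesis of 0.5", and the null is rejected if the upper limit of the two-sided 95% CI lies below 0.5.

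The same section adds a switch. If the negative binomial model does not converge, or "if the AIC in the model accounting for zero-inflation is lower, then the zero-inflation negative binomial model will become the primary objective analytic model". For that model it describes only unconditional ABR estimates per cohort.

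**The concern.** Three things that define a primary test differ: the effect measure (difference or ratio), the null (no difference or a ratio of 0.5) and the model (t-test or negative binomial). The two nulls are far apart, so one data set can meet one rule and miss the other.

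This does not depend on setting protocol against SAP. Protocol 10.1 names a negative binomial model and 10.3.6.1 a t-test. Protocol 10.1 and SAP 7.9.3 then state opposite nulls for the same endpoint.

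The switch adds a second problem. AIC and convergence are judged on outcome data, and if the two-part model takes over, the plan gives no interval or test of its ABR ratio against 0.5. The success rule is then undefined.

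**Working it through.** **Inputs** (Protocol 10.1, SAP 7.6): SoC ABR 3, Roctavian ABR 0.85 (ratio 0.283), dispersion 1.5, θ = 0.2, exposure 1 year, null ratio 0.5, one-sided 2.5%, power 80%. Planned follow-up is 3 years (Protocol 5.1).

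**1. Reproduce the stated sample size** (SAP 7.6 formula, fixed marginal total variance)
- V1 = 1/3 + 1/(0.2 × 0.85) + 1.2 × 1.5/0.2 = 15.216
- V0 = (1 + 0.5 × 0.2)² / [0.5 × 0.2 × (3 + 0.2 × 0.85)] + 9 = 12.817
- ln 0.5 − ln 0.2833 = 0.568
- N1 = (1.96√12.817 + 0.842√15.216)² / 0.568² = 328.8; N2 = 0.2 × 328.8 = 65.8

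Rounded up, this is 329 + 66 = 395, against the stated 330 + 67 = 397. Power at 330/67 is 80.6%. With a null ratio of 1 the same formula gives 61.2 and 12.2, that is 62 + 13 participants. The stated size therefore belongs to the ratio test against 0.5.

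**2. Where the SAP rule succeeds**

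SE(log RR) = √[(1/(3T) + 1.5)/330 + (1/(0.85T) + 1.5)/67], which is 0.213 for T = 1 year and 0.182 for T = 3 years. The upper limit is below 0.5 when the observed ratio is below 0.5 × exp(−1.96 × SE): 0.33 at 1 year and 0.35 at 3 years. Recomputing the SE at the boundary rate gives 0.333 and 0.352.

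**3. Where the protocol t-test succeeds**

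The variance of an individual ABR with mean m is v(m) = m/T + 1.5m². The boundary is the ratio r at which 3(1 − r) / √[v(3)/330 + v(3r)/67] = 1.96.

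| Follow-up | Welch | Pooled variance |
|---|---|---|
| 1 year | 0.72 | 0.66 |
| 3 years | 0.74 (0.73 with the t quantile) | 0.68 |

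**4. One example.** Observed ABRs of 3.0 and 1.2 at 1 year. The difference is 1.8 with SE √(16.5/330 + 3.36/67) = 0.316, so t = 5.7: success under Protocol 10.3.6.1. The rate ratio is 0.40 with SE(log) 0.201 and 95% CI 0.27 to 0.59: failure under SAP 7.9.3.

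**5. How often the rules disagree.** Simulation with 2,000 gamma-Poisson data sets per row, 330/67, SoC ABR 3, dispersion 1.5, no weighting. The first three columns of results are for 1 year; disagreement is counted with the Welch test.

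| True ratio | t-test succeeds (Welch / pooled) | NB against 0.5 succeeds | Disagree, 1 year | Disagree, 3 years |
|---|---|---|---|---|
| 0.283 | 100% / 100% | 80% | 20% | 10% |
| 0.40 | >99.9% / 99.5% | 20% | 80% | 76% |
| 0.50 | 97.6% / 93.6% | 3% | 94% | 95% |
| 0.60 | 85% / 70% | 0.3% | 85% | 90% |

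Every disagreement was a t-test success with a negative binomial failure. The reverse did not occur.

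**The case against.** Protocol 10.3 calls itself a summary and leaves technical detail to the SAP, and 10.3.1 lists negative binomial models for bleeding variables. One could therefore treat SAP 7.9.3 as the operative text. That softens the conflict but does not resolve it: a summary may omit detail, but 10.3.6.1 states a different test and 10.1 an opposite null.

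It is also fair that 10.1 confines the shifted null to sample size deliberately, so 0.5 is not the only coherent choice. What must be corrected is the contradiction; the preference for 0.5 rests on the sample size.

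Three stronger readings should be resisted.
- A reader might infer that the choice between t-test and negative binomial would be made after the comparative interim results. Protocol 10.3 has the SAP finalised before the data cut for the 18-month analysis. Only the AIC and convergence switch depends on outcome data.
- A reader might infer that the disagreement could favour either rule. At the planning values it runs one way only.
- A reader might count the general 0.05 significance level in SAP 7.9 as a further conflicting rule. It agrees with a two-sided 95% CI and contradicts nothing.

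Averaging individual ABRs also gives short and long follow-up equal weight. Little loss is expected over a fixed 3 years (Protocol 8.2), so this matters mainly at interims and under hypothetical-estimand censoring. It is secondary here.

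**Conclusion.** The contradiction stands and must be resolved. An observed rate ratio between about 0.33–0.35 and about 0.66–0.74 meets the protocol rule and fails the SAP rule. The upper end depends on the t-test variant, and both ends depend on 1 or 3 years of exposure. At the planned effect this affects 10–20% of data sets; at true ratios of 0.40 to 0.60 it affects 76–95%. The 80% power and the 397 participants are claims about the ratio test against 0.5 and cannot be carried over to the t-test.

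These figures assume an SoC ABR of 3, dispersion 1.5, cohorts of 330 and 67, equal exposure and no weighting, so they are approximate. IPTW would widen the intervals and move the limits, but it cannot reconcile a null of no difference with a null of 0.5.

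**What to change.** Name one effect measure, one model and one null in Protocol 10.1, Protocol 10.3.6.1 and SAP 7.9.3. The choice that fits the stated sample size is:

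- Primary: the IPTW-weighted negative binomial rate ratio with log follow-up offset, tested one-sided at 2.5% against 0.5. Replace the t-test in 10.3.6.1 and remove the not-shifted sentence in 10.1 for the primary endpoint.
- Delete the AIC switch. Keep the two-part model and the mean ABR difference as sensitivity analyses.
- Pre-specify a fallback for non-convergence, with its own interval and test of the ABR ratio against 0.5.
- State which measure and null apply to the major, life-threatening and joint ABRs, because Protocol 10.3.7.1 ties them to the primary analysis.

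If the sponsor prefers the unshifted null, the SAP success rule must go and the sample size justification must be restated, since the 397 participants then no longer follow from it.

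The cost is a wording amendment with no new data. The price of the recommended choice is a stricter success criterion than Protocol 10.1 now states, but it is the one the study was sized for.

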10.3.7. Secondary Objectives

10.3.7.1. Objective: To compare the annualized bleeding rate for major, life threatening, and joint bleeds.

ABRs for other bleeding outcomes described in [Table 6](#) (major bleeds, life-threatening bleeds and joint bleeds) will also be compared between the Roctavian Cohort and SoC Cohort after PS adjustment. The analysis approach will be consistent with the primary objective (see Section [10.3.6](#)) regarding PS adjustment approach, analysis of the full follow-up time along with annual increments, as well as measurement of treatment effect.

10.3.7.2. Objective: To compare the proportion of participants with zero bleeds for treated, major, life threatening, and joint bleeds.

Proportion of participants with zero bleeding events for all bleeding outcomes described in Table 6 will be compared between the Roctavian Cohort and SoC Cohort after PS adjustment, generally consistent with the analysis approach for ABRs (see Section 10.3.6 above) regarding PS adjustment approach, analysis of the full follow-up time along with annual increments, as well as, start of bleed follow-up and censoring reasons.

Differing from the approach for ABRs, analyses of the proportion of participants with zero bleeding will only include those participants with follow-up for the full time over which the proportion is calculated. Additionally, the measurement of treatment effect for these analyses will be the relative risk and 95% confidence interval between participants in the Roctavian Cohort and SoC Cohort having zero bleeding events.

10.3.7.3. Objective: To compare the use of hemostatic medications.

The use of hemostatic medications will be compared between the Roctavian Cohort and SoC Cohort after PS adjustment, generally consistent with the analysis approach for ABRs (see Section 10.3.6 above) regarding PS adjustment approach, and analysis of the full follow-up time along with annual increments. Comparisons will be made regarding the variables in Table 7.

The proportion of participants utilizing any hemostatic treatments during follow-up will be described but will not be compared as 100% of the SoC Cohort will utilize hemostatic treatments. The relative risk of participants utilizing any hemostatic treatments specifically for bleeds or short-term prophylaxis will be compared consistent with the proportion of participants with zero bleeding events. Also consistent with the analysis of the proportion of participants with zero bleeding, only those participants with follow-up for the full time over which the proportion is calculated will be included in analyses.

The total FVIII per kg administered during follow-up will be compared between the cohorts. Total FVIII per kg for any reason will be compared based on the absolute difference in the mean total FVIII per kg between the Roctavian Cohort and SoC Cohort utilizing a two-sample t-test (two-sided). Similar to the analyses of the proportion of participants with zero bleeding, only those participants with follow-up for the full time over which the proportion is calculated will be included in analyses.

Annualized infusion rates (AIRs) will also be compared between the cohorts. AIRs will be calculated for each participant as the number of infusions or injections divided by the time between the start of follow-up and censoring event for the analysis, annualized to the number of infusions/injections in 1 year. The mean of the individual participant AIRs for each cohort will be calculated and compared. The comparison of AIRs will be based on the absolute difference in the mean AIR between the Roctavian Cohort and SoC Cohort utilizing a two-sample t-test (two-sided).

10.3.7.4. Objective: To compare joint health, quality of life, and pain.

Descriptive statistics will be used to summarize the absolute and change from baseline at the time of assessment for the HJHS. A repeated measurement analysis model will be utilized to describe the overall trend in the HJHS over time. The mean change from baseline to final assessment approximately 3 years after index date will be compared between the Roctavian Cohort and SoC Cohort.

Descriptive statistics will be used to summarize the absolute and change from baseline at the time of an assessment for the total and domain scores for the Haemo-QoL-A and the BPI-SF. For the BPI-SF the pain interference and pain intensity scores will be taken as the domains. A repeated measurement analysis model will be used to compare the changes in scores between the treatment groups. Participants with an evaluable baseline score and at least one evaluable post-baseline score will be required for the specific analysis be included in the change from baseline analyses.

In addition, responder analyses will be considered for improvement and deterioration for the BPI-SF pain interference and pain intensity scales. The BPI-SF pain intensity score will be defined as the Question 5 “average pain”. The BPI-SF pain interference score will be defined as the average to all 7 subitems of Question 9 (9A to 9G).

All analysis details and scoring methods will be described in the SAP. It is expected that no missing data will be imputed.

All PROs comparisons will be interpreted after 3 years of follow-up, or latest available follow-up score if a full 3 years of follow-up is not available.

10.3.7.5. Objective: To compare safety events of interest.

Safety events outlined in [Table 8](#) will be described in each cohort. Summaries of the proportion, event rate, and incidence rate of each of the safety events among all participants by cohort will be provided. Safety events will be described from index through follow-up. All participants will be included in analyses of event and incidence rates, while analyses of the proportion of participants will only include those participants with follow-up for the full time over which the proportion is calculated. Safety outcomes will be compared as relative risks based on the incidence of an event for analyses of the treatment policy estimand and as incidence rate ratios censoring a participants person time at the time of the event for analyses of the hypothetical estimand.

10.3.7.6. Objective: To describe time to resumption of prophylactic treatment among participants administered Roctavian

Time between Roctavian administration (index date) and resumption of hemostatic prophylaxis (defined in [Table 7](#)) will be described for the Roctavian Cohort only. The proportion who return to prophylaxis and time to resumption will be described among those in the cohort who ended prophylaxis post Roctavian administration. Summary statistics will

be utilized to describe time to resumption including mean (SD), median (inter quartile range), minimum and maximum. Treatment utilization patterns in the 3 and 6 months after the resumption of prophylaxis will be described regarding the number of infusions/injections by prophylaxis treatment class, total FVIII dose for participants returning to prophylaxis with FVIII, and frequency of infusions/injections will be described.

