7.2.5.4. Hemophilia Joint Health Score

The HJHS is a validated outcome tool developed for the assessment of joint health in people with hemophilia (Feldman 2011). The ordinal joint score assesses 9 items in 6 index joints. The HJHS measures joint health, in the domain of body structure and function (ie, impairment), of the joints most commonly affected by bleeding in hemophilia: the knees, ankles, and elbows. This physical examination assessment tool conducted by a healthcare provider is sensitive enough to pick up the subtle early signs of joint damage. It is appropriate for monitoring joint change over time or assessing efficacy of treatment regimens in children receiving both prophylactic and on-demand therapy.

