Descriptive statistics (mean, SD, median, IQR, minimum, maximum) will be used to summarize the COA scores at baseline, follow-up, and change from baseline. Two-sided t-tests will be used to compare the absolute change in scores from baseline between Roctavian and SoC Cohorts. Distribution of the outcome variables will be checked to make sure the assumptions of the two-sided t-test are met. If a skewed distribution is observed, a non-parametric Wilcoxon signed-rank test will be performed instead. SMD of the scores at baseline, follow-up, and change from baseline between the Roctavian and SoC Cohorts will also be estimated as the effect size measure.⁴⁸ SMD values will be classified into small, medium, large or very large based on the following ranges, 0.2-0.5, 0.5-0.8, 0.8, and ≥1.3.

Participants with an evaluable baseline score and at least one evaluable post-baseline score will be included in the change from baseline analyses. Since participants are expected to have follow-up visits every 6-months for Haemo-QoL-A and BPI-sf and annual follow-up visits for HJHS, it is expected that COAs will be measured with a maximum of seven time points for Haemo-QoL-A and BPI-sf (baseline, 6±3, 12±3, 18±3, 24±3, 30±3, and 36±3 months) and four time points (baseline, 12±3, 24±3, and 36±3 months) for HJHS. The last follow-up measure will be used in the change from baseline analysis. The last follow-up measure may be required to have occurred at least a certain

number of years after baseline to increase interpretability of results. A general linear mixed model with unstructured covariances will be fit to conduct a longitudinal analysis for each COA outcome. The mixed model is chosen to account for the repeated measures, while allowing flexibility for any potential missing values. No missing data will be imputed. The explanatory variables that will be included in the model are treatment (Roctavian vs. SoC) and time. Treatment by time interaction will also be included in the model to assess whether the treatment effect changes across time. Residual analysis will be conducted to ensure the independent and identically distributed random variables assumptions of the model residuals are met. Regression coefficients, 95% CIs and P-values for each of the fixed-effects parameters will be reported. Estimated correlation matrix will also be reported to assess the correlation of the outcome between each time point.

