For all the COA outcomes described above, both the unweighted and IPTW weighted analyses will be conducted. SMD will be computed to compare the outcomes between Cohorts. P-values for each corresponding statistical test will also be reported.

In addition, a responder analysis will be considered for the COA improvement and deterioration of the six joint health scales to understand the magnitude of observed clinically meaningful effects. A responder analysis is defined as an analysis or presentation of the proportion of participants who achieved a pre-defined level of improvement on one of the main outcomes at a certain time point.⁴⁹ Based on IQWiG's guidance for responder analysis, (a 15% change of the scale range)⁵⁰, participants with a deterioration and improvement (reported separately) in their scores of 15% (e.g., 15% of a 10 point scale is 1.5) from the baseline to the latest follow-up measure will be defined as responders. All other participants will be defined as non-responders. The binary outcome (responder versus not) will be analyzed using propensity score IPTW weighted log binomial regression models. The main predictor of interest is the treatment effect (Roctavian vs. SoC), other imbalanced covariates after propensity score adjustment may be included in the model as necessary. The risk ratio (relative risk), corresponding 95% CIs and p-values will be reported.

To visually represent the responder analysis results and to aid in its interpretation, The response rate at each time point will be plotted as response curves for each COA by study Cohort to illustrate the change in response rate across time.

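### Change-from-baseline and responder analyses of joint health, quality of life and pain use each participant's last score whatever its timing, so follow-up length can mix with treatment effect; for HJHS the protocol and SAP also disagree

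*Protocol*

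**What the plan says.** **PROs.** Protocol section 10.3.7.4 states: "All PROs comparisons will be interpreted after 3 years of follow-up, or latest available follow-up score if a full 3 years of follow-up" cannot be reached. One post-baseline score is enough to enter the change analysis. The same section plans a repeated-measures model to compare changes between cohorts and adds: "It is expected that no missing data will be imputed".

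**HJHS.** Section 10.3.7.4 says: "The mean change from baseline to final assessment approximately 3 years after index date will be compared". It gives no fallback, and the repeated-measures model is there only to describe the trend. The PRO sentence does not reach HJHS, which section 7.2.5.4 describes this way: "This physical examination assessment tool conducted by a healthcare provider".

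**All clinical outcome assessments.** SAP section 7.9.4.4 covers HJHS, Haemo-QoL-A and BPI-SF together. For the change analysis: "The last follow-up measure will be used in the change from baseline analysis". The test is a two-sided t-test of change, with no time term. For the responder analysis, participants with a 15% change "from the baseline to the latest follow-up measure will be defined as responders". The only guard on timing is conditional and has no number: "The last follow-up measure may be required to have occurred at least a certain" number of years after baseline. The same section plans a linear mixed model with treatment, time and treatment-by-time terms, run unweighted and IPTW-weighted.

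**Follow-up.** Protocol section 5.1 designs for 3 years per participant. Under the hypothetical estimand (section 10.3.2.3), Roctavian participants are censored when they resume prophylaxis, and SoC participants when they receive Roctavian. SAP section 7.9.6 expects variable follow-up at the 36- and 54-month interims.

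**The concern.** The question asked is change at about 3 years. A last-score analysis answers it only for participants who reach 3 years. For the others it enters a change measured earlier, and the t-test and responder proportion treat all these changes as one quantity.

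This matters where the cohorts differ in follow-up. Under the hypothetical estimand a Roctavian participant who resumes prophylaxis contributes the last score before resumption. At interims, follow-up depends on when each cohort enrolled, and protocol section 10.4 plans full interim analyses of all endpoints. A time trend is plausible at least for joints: protocol section 3.1.1 says joint bleeds that occur despite prophylaxis may lead to deterioration.

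The plan is stricter elsewhere. Zero-bleed proportions and total FVIII per kg are restricted to participants with full follow-up for the period (sections 10.3.7.2 and 10.3.7.3). SAP table shells 10 to 12 show one follow-up block and one change block per instrument, with a row comparing length of follow-up between cohorts. They report unequal follow-up without keeping it out of the comparison.

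**Working it through.** **1. Spread of times that can be pooled.** SAP Table 8 puts the 6-month window at days 92 to 273, the 12-month window at days 274 to 456 and the 36-month window at days 1,004 to 1,185. With 365.25/12 = 30.44 days per month, 92/30.44 = 3.0 months and 1,185/30.44 = 38.9 months. On the annual HJHS schedule the earliest window starts at 274/30.44 = 9.0 months, although SAP section 7.9.4.4.1 also speaks of six-monthly HJHS capture.

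**2. Cohort sizes.** No figure is given for these endpoints, so I use 67 and 330 from the primary-endpoint calculation. The SAP section 7.6 formula gives V0 = 12.817, V1 = 15.216 and N1 = 328.8, hence 329 + 66 = 395 against the stated 397. That is close enough to take 67 and 330 as given.

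**3. Bias with no treatment effect.** Assume a shared linear drift of b SD of change over 3 years, and that a share f of a cohort has its last score at t years.

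- Mean last-score time = 3(1 − f) + f·t
- Spurious difference d = b × (difference in mean time)/3
- SE = √(1/67 + 1/330) = 0.134 SD
- Type I error = 1 − Φ(1.96 − d/SE) + Φ(−1.96 − d/SE)

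Worked case, 30% (Roctavian) against 5% (SoC) stopping at year 1: mean times are 3(0.70) + 0.30 = 2.40 and 3(0.95) + 0.05 = 2.90 years. For b = 0.5, d = 0.5 × 0.50/3 = 0.083 SD, d/SE = 0.62 and type I error is 9.5%.

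| Short follow-up, Roctavian vs SoC | Last score | Mean time (years) | d for b = 0.25 / 0.5 / 1.0 | Type I error |
|---|---|---|---|---|
| 10% vs 10% | 1.5 y | 2.85 vs 2.85 | 0 / 0 / 0 | 5% throughout |
| 20% vs 5% | 1.5 y | 2.70 vs 2.92 | 0.019 / 0.037 / 0.075 | 5.2 / 5.9 / 8.7% |
| 30% vs 5% | 1 y | 2.40 vs 2.90 | 0.042 / 0.083 / 0.167 | 6.1 / 9.5 / 23.8% |
| 40% vs 5% | 1 y | 2.20 vs 2.90 | 0.058 / 0.117 / 0.233 | 7.2 / 14.0 / 41.4% |

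With b = 0, every row gives d = 0 and 5%.

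**4. Simulation check** (4,000 runs, 30% vs 5% stopping at year 1 independently of outcome). Last-score differences (Roctavian minus SoC) were −0.084 and −0.167 SD for b = 0.5 and 1.0, with rejection in 9.0% and 23.1% of runs. Comparing only those with a 36-month score gave differences of −0.002 and −0.003 SD and rejection in 4.9% and 5.4%. This shows the effect of fixing the visit; the mixed model itself was not fitted.

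**The case against.** Much of the case on the other side stands.

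- **A time-aligned comparison is already planned.** The PRO comparison in section 10.3.7.4 is a repeated-measures model, and the SAP model has a treatment-by-time term for every instrument. The SAP also plots response rates at each visit. The fault lies in the last-score t-test, the responder rule and the PRO interpretation sentence. No text names a month-36 model contrast as the result.
- **The route to unequal follow-up is limited.** Under the treatment policy estimand, which the G-BA required, participants who resume prophylaxis stay in. Everyone is designed to have 3 years, and protocol section 8.2 does not anticipate loss to follow-up. What remains is mainly the hypothetical estimand and the interims.

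Four stronger readings are tempting, and the documents do not support them.

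- **That the protocol's fallback sentence covers joint health.** It covers PROs only. For HJHS the issue is a mismatch between the protocol and SAP section 7.9.4.4.
- **That the bias favours Roctavian.** That needs steady deterioration. No shared trend is stated for Haemo-QoL-A (4-week recall) or BPI-SF (24-hour recall), and if Roctavian participants improve gradually, an early last score understates the benefit.
- **That the rule breaks the no-imputation statement.** The endpoints are defined on observed scores, no 36-month value is created, and the statement is hedged.
- **That false-positive rates of 13% to 45% should be expected.** Such rates arise from assuming 1 HJHS point per year with slope SD 0.5 and measurement SD 1.0. The 3-year change SD is then √(1.5² + 2 × 1.0²) = 2.06, so the drift is 3/2.06 = 1.46 SD, for which the documents give no basis.

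**Conclusion.** The concern holds in limited form. The last-score rule is stated, its only timing guard has no value, and it pools changes measured at very different times. With both a time trend and unequal follow-up, the comparison mixes follow-up length with treatment effect. If either is absent, the bias is zero.

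The size cannot be fixed from the documents. Over the assumed ranges, type I error runs from 5% to about 41%, and the 30% against 5% case is an illustration, not a forecast. SAP section 7.9 makes secondary p-values nominal, so this distorts reported effects and does not breach confirmatory error control. The primary endpoint and the sample size are unaffected. The plan should be changed because joint health, quality of life and pain are stated comparative objectives.

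**What to change.** In protocol section 10.3.7.4 and SAP section 7.9.4.4:

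1. Make the month-36 Roctavian-minus-SoC contrast from the planned weighted mixed model the interpreted comparison for HJHS, Haemo-QoL-A and BPI-SF, with a named earlier visit at each interim.
2. Define responders at that same fixed visit, using observed scores.
3. Reconcile the HJHS comparison in the protocol (about 3 years) with the last-score rule in the SAP.
4. Keep last-available change as descriptive or sensitivity analysis only, and drop the open-ended minimum time.

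The model is already planned, so the cost is mostly wording. Intervals will be somewhat wider, and fewer participants will enter the fixed-visit responder analysis. Imputing missing responder status would be a further step that departs from the SAP's no-imputation rule for these outcomes; it is not needed here. The fixed-visit contrast does not by itself remove informative censoring at resumption of prophylaxis, which should be stated as a limitation of the hypothetical estimand.
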